### 2.3 Proposed timing of the intervention

The NICE guidelines advise that RTW interventions should be delivered between two and six (and a maximum of 12) weeks into a period of sickness absence (National Institute for Health and Care Excellence 2009). Waddell and Black advise that the intervention should be delivered after four weeks of absence (Waddell, Burton 2004, Black, Frost 2011). Previous UK studies on interventions for all causes of sickness absence have intervened after workers have been absent for four weeks, Smedley et al. 2013) and one day (Demou, et al,2015). Smedley's choice was based on the evidence from Waddell (Waddell, Burton 2004) on the pattern of RTW albeit in all cause absence or musculoskeletal disorders.

The EASY study intervention at day one was by telephone and based on the management of sickness absence in 'commercially successful companies' (Demou et al, 2015). The recommendations from Waddell, Black and NICE (Black, Frost 2011, Waddell, Burton 2004, National Institute for Health and Care Excellence 2009) were based on data relating to all causes of sickness absence, with the premise that most workers who take sick leave RTW within four weeks without intervention. In contrast, the Dutch guidelines on RTW after absence due to mental ill health advise that the intervention should take place two weeks into the absence (van der Klink et al. 2007) and on-going trials of interventions to improve RTW after sickness absence due to CMHD are intervening at 'about two weeks' (van Beurden 2013) and before three months of sick leave ([name], personal correspondence).

In considering the timing of the intervention for our study, we looked at two sets of data from NHS workers off sick with mental health problems. The NHS electronic staff record (ESR) has a code (S10) for sickness absence due to anxiety/stress/depression and mental illness. We obtained all staff sickness absence data for code S10 at Guy's and St Thomas' NHS Foundation Trust for 2015 (this included three staff members whose sickness absence for mental illness commenced in 2014). The corresponding Kaplan-Meier survival curve shows that approximately 30% of staff who were on sick leave with mental illness at Guy's and St Thomas' NHS Trust between 1 January- 30 November 2015 returned to work within one week (see: Figure 1). At the Trust, there is currently no policy for intervention until day 27 of sickness absence.

Figure 1

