At three trusts the departmental groups will be assigned either: a) to see an OH nurse who has been trained as a case-manager and receive the intervention; or b) to see an OH nurse who has not been trained as a case-manager and receive care as usual for that trust (mixed intervention/care as usual sites). At two trusts, no OH nurses will have been trained as case managers and all participants from the departmental groups will receive care as usual for that trust (care as usual sites). At one trust, participants will see an OH nurse who has been trained as a case-manager and receive the intervention (intervention only site). We will recruit 77 participants. Thus, there will be four groups of participants.

- 21 participants from departmental groups will receive the intervention from study centres delivering the intervention or care as usual (Group A)
- 21 participants from departmental groups will receive care as usual from study centres delivering the intervention or care as usual (Group B)
- 28 Participants from departmental groups will receive care as usual from centres delivering only care as usual (Group C)
- 7 participants from departmental groups will receive the intervention from study the centre delivering the intervention (Group D)

Table 1: Recruitment targets per site				
Participating site	Intervention	Care as usual		
Care as usual sites				
Guy's and St Thomas NHS Foundation Trust	N/A	14 (Group C)		
West Midlands Ambulance Service	N/A	14 (Group C)		
Mixed intervention/ care as usual sites				
The Ipswich Hospital NHS Trust (acute and ambulance)	7 (Group A)	7 (Group B)		
Norfolk and Norwich NHS Foundation Trust (acute)	7 (Group A)	7 (Group B)		
University Hospitals Leicester NHS Trust (acute)	7 (Group A)	7 (Group B)		
Intervention site				
Papworth Hospital NHS Foundation Trust (special)	7 (Group D)	N/A		

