We will collect the same data on all participants and participating centres. Data from all groups will be used to answer questions about rates of recruitment and follow-up, and the acceptability and performance of methods to assess possible outcome measures. Data from Group A and Group D will provide information about the acceptability and costs of the intervention, and rates of adherence to the intervention. Data from Groups B and C will provide information about the distribution of possible outcome measures in the absence of the intervention (which would help in power calculations for a subsequent trial). Comparison of the management of participants in Groups B and C will give an indication of potential for major "contamination". The follow-up period will be six months from recruitment. Outcomes will be assessed using a mix of qualitative and quantitative methods.

Target population: NHS staff who have recently commenced sick leave because of CMHD

**Inclusion criteria:** Staff with CMHD with or without an associated physical disorder who have been off sick for a period of more than 7 days (i.e. on receipt of fit note) and less than 90

days. Staff will be screened for eligibility for entry into the study either at the time of referral to OH or during their 1st OH appointment.

**Exclusion criteria:** Staff with a psychotic disorder, bipolar disorder, substance abuse or dementia. Staff under formal investigation for misconduct or in the formal process of disciplinary action (as this may be an effect modifier).

Six OH departments have been chosen from those confirming that they wished to participate in the feasibility study in response to the questionnaire sent to the current SCIN study centres plus one ambulance trust. We have selected NHS OH departments representative of the range of NHS Trusts in the UK, providing OH services to a mixture of acute, mental health and ambulance trusts. All trusts included have electronic OH data capture systems, do not currently have early (<8 day) intervention for sickness absence or case-management in use and employ more than two OH nurses who advise on RTW in workers with CMHD.

We have allocated the participating trusts to care as usual or mixed intervention/ care as usual centres / intervention centre based on sampling groups with the aim of achieving broad comparability between the types of trust.

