# 6.3 Recruitment and sampling:

Before recruitment commences, we will train the centres on how we wish to collect sickness absence data from ESR. We will assist participating OH departments to liaise with their HR departments to ensure that the HR departments accurately record fit notes reporting CMHD onto S10 of the ESR system.

In the study centres where participants receive either the intervention or usual care, two OH nurses will recruit participants at each centre. Up to two OH nurses will be trained in case management and will deliver the intervention and the other will deliver care as usual for that trust. The duration of recruitment will be 6 months. Where possible, all staff who go on sick leave with CMHD during the 6 month recruitment period will be referred to the OH department as soon as their line manager receives a fit note. We will provide sites with wording to further raise the profile of OH and their local site's involvement in the study. The decision on whether to circulate this correspondence will be left to participating sites. The study will also recruit from those who self-refer to Occupation Health departments. All staff who go off sick with CMHD and who are referred to the participating OH departments will be provided with information about the study and invited to participate. Those who wish to participate will be asked to consent and will be screened for eligibility for the study. At the discretion of the participating study centres, participants in the intervention group will continue to receive the

intervention until they RTW or leave their employment, even if they are still on sick leave after the study has finished.

At one study centre (Guy's and St Thomas' NHS Foundation Trust; GSTT) we would like to promote the role of occupational health service in manging workers who are on sick leave due to common mental health conditions. We would like to add a brief message about the role of OH and about the Ways Back to Work study to the Workforce Directorate brief which is correspondence disseminated across the GSTT trust only targeting line managers.

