# 6.5.1 Quantitative

Rates of recruitment will be calculated from the numbers of eligible participants and of those who agree to participate in the study. Characteristics of eligible participants will be recorded at baseline and will be summarised through means, medians, standard deviations, and interquartile ranges (IQRs). Characteristics will be compared between those who agree to participate in the feasibility study and those who do not. Outcome variables, including anxiety/depression score, health related quality of life score, use of antidepressants, will be summarised separately for baseline and follow-up using means and standard deviations if they are normally distributed, or through medians and IQRs otherwise. Number of days before returning to normal working hours will be summarised by medians and IQRs. For each possible outcome measure, the prevalence of missing data will be quantified. We will calculate the proportion of participants who complete the intervention, and the proportion of completed data sets.

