### 6.6 Sample size

We calculated that with a sample size of 60 we will be able to estimate a participation rate of 80% to within a 95% confidence interval of +/- 10%. We have allowed for a maximum of 77 participants so we are confident that we will have a good precision around the participation, and completion rates. All the OH departments who have confirmed that they wish to take part would expect to see more than 20 workers who go on sick leave with CMHD in a six-month period. Therefore, we consider that it is feasible to recruit 14 participants at care as usual and mixed intervention/care as usual centre and 7 participants at the intervention only centre.

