### 7.0 Phase 2:

Finalisation of the manualised intervention and recommendations for design of a RCT

**Method:** We will work with our stakeholder group including our PPIs to review the information from the feasibility study and determine whether a cluster RCT could be designed that was free from unacceptable contamination. We will review the findings from qualitative, quantitative and economic analyses. We will pay particular attention to the response rate, and likelihood of contamination to determine if an individual or cluster trial would be the most appropriate method for a definitive trial.

Should a RCT be judged feasible, data from the feasibility study on the distribution of relevant outcome measures in the absence of intervention will help to inform power calculations.

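### Group B is labelled free of the intervention for the future power calculation while its contamination is still being tested, and the section 6.5.1 summaries do not yield the change that section 6.4.1 names

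*Protocol*

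**What the plan says.** **Source of the control inputs.** In the study design part of section 6.1 the protocol says "Data from Groups B and C will provide information about the distribution of possible outcome measures in the absence of the intervention" and gives power calculations for a later trial as the use. Section 7.0 repeats this: "data from the feasibility study on the distribution of relevant outcome measures in the absence of intervention will help to inform power calculations". Section 6.1 places Group B (21 people) at the three mixed trusts and Group C (28 people) at two trusts where no nurse is trained as a case manager. Directly after naming B and C as the source, it says that the management of B and C will be compared to gauge contamination. Question 7 in section 4.1 lists within-trust contamination as unanswered.

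**Care in the control groups.** Section 6.3 says that staff off sick with a common mental health disorder, where possible, "will be referred to the OH department as soon as their line manager receives a fit note". No arm is excepted. The study flowchart adds an occupational health (OH) call within 3 working days of referral where possible. Section 6.3 also offers all sites optional wording to promote OH, and plans a further message to line managers at Guy's and St Thomas', which supplies 14 of the 28 in Group C. Of that trust, section 2.3 says "At the Trust, there is currently no policy for intervention until day 27 of sickness absence".

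**Summaries.** Section 6.4.1 names reduction in anxiety/depression and change in antidepressant use among the outcomes whose distribution is wanted. Section 6.5.1 says that outcome variables, with antidepressant use in the list, "will be summarised separately for baseline and follow-up using means and standard deviations if they are normally distributed, or through medians and IQRs otherwise". Days to normal working hours get medians and IQRs.

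**The concern.** Two things do not fit together.

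First, the protocol describes B and C jointly as showing outcomes without the intervention, while one of its own questions is whether that is true of B. It gives no rule for the power inputs if the comparison shows contamination. If some of Group B did receive parts of the intervention, control outcomes that include them would not describe untreated care. In both groups, referral timing and OH promotion may also differ from what the trusts did before, so care as usual here may not be prior usual care.

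Second, section 6.4.1 names outcomes as change, but section 6.5.1 fixes summaries by time point. Those tables do not contain the quantities needed to size a comparison of the clinical scores that uses baseline. For a yes/no item, the stated rule loses the proportion, which is the figure a later trial would need.

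Informing the next trial is the purpose of Phase 2, so the form of these inputs matters more here than the descriptive tables of a small study usually would.

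**Working it through.** **1. The plan's own figure.** Section 6.6 says that "with a sample size of 60 we will be able to estimate a participation rate of 80" per cent to within 10 points either way. The normal-approximation half-width is 1.96 × √(0.8 × 0.2 / 60) = 10.1 points; exactly 10 points needs 1.96² × 0.16 / 0.01 = 61.5, so 62. The stated 60 reproduces within rounding. It concerns participation only. No precision is stated for any input to the later power calculation.

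**2. Group sizes (section 6.1 and Table 1).** A 21 + B 21 + C 28 + D 7 = 77, matching "We have allowed for a maximum of 77 participants". Controls are B + C = 49, and B is 21/49 = 43% of them.

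**3. What contamination of B would do to a combined figure.** Suppose a fraction c of Group B received the full effect δ (assumed; the documents give no value). The combined mean then moves by c × 21/49 × δ.

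| c (assumed) | Shift, as share of δ |
|---|---|
| 10% | 4% |
| 20% | 9% |
| 30% | 13% |
| 50% | 21% |

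With Group C shown apart, this shift would be absent from C's figures.

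**4. What separate time-point summaries leave out.** The variance of change is s₀² + s₁² − 2·r·s₀·s₁, where s₀ and s₁ are the baseline and follow-up SDs and r is their correlation. Separate tables give at most s₀ and s₁, and neither if the scores are skewed. They do not give r. For illustration, take a standardised difference of 0.3, 90% power, two-sided 5% and equal SDs (all assumed). Follow-up scores alone need 2 × (1.960 + 1.282)² / 0.3² = 233.5, so 234 per arm. Baseline adjustment multiplies this by (1 − r²), and change scores by 2(1 − r).

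| r (assumed) | Baseline-adjusted, n per arm | Change score, n per arm |
|---|---|---|
| 0.3 | 213 | 328 |
| 0.5 | 176 | 234 |
| 0.7 | 120 | 141 |

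The section 6.5.1 tables cannot narrow this range. The paired questionnaires at 0, 3 and 6 months could.

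**5. The yes/no item.** If antidepressant use is coded 0/1 it is never normal, so the rule leads to median and IQR. True rates of 30% and 40% both print as median 0, IQR 0 to 1; rates of 60% and 70% both print as median 1, IQR 0 to 1.

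**6. Cost of showing the groups apart.** The 95% interval for an SD, as a multiple of its estimate, is √((n − 1)/χ²) at the 97.5% and 2.5% points of χ² on n − 1 degrees of freedom. The implied sample size scales with the square.

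| Group | n | SD factor | Sample-size factor |
|---|---|---|---|
| B + C | 49 | 0.83 to 1.25 | 0.70 to 1.56 |
| C | 28 | 0.79 to 1.36 | 0.63 to 1.85 |
| B | 21 | 0.77 to 1.44 | 0.59 to 2.09 |

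These assume complete follow-up and roughly normal data. With 20% loss (assumed), the sample-size factors are 0.67 to 1.66 for B + C (n = 39) and 0.59 to 2.04 for C (n = 22).

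**The case against.** The case on the other side is substantial, and several stronger readings fail against it.

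- **A reader might infer that neither control group is free of the intervention.** The documents do not support that. Group C has no trained case managers by design. Group B sees nurses without that training, so it is at risk of contamination and is not shown to be contaminated.
- **A reader might infer that B and C must be merged.** No section orders a single combined estimate. Section 7.0 reviews contamination before recommending a design, and says only that the data help to inform the calculation. This stands, but no section says what follows for the inputs.
- **A reader might infer that early referral makes the controls unrepresentative.** It is qualified as where possible, and nothing in the documents shows that it speeds return to work. If the definitive trial used the same route, this would be its control care too. What stands is that the change from prior practice should be described.
- **A reader might conclude that C alone should be the main input.** C is one acute and one ambulance trust, 14 each, while the trial is meant for a variety of trusts and section 6.1 says ambulance trusts have the highest sickness absence. Nor is a historical staff-record extract a necessary substitute: code S10 also covers other psychiatric illness and staff who would never have been eligible.
- **A reader might think that change and correlation cannot be obtained.** The paired data allow both, and section 2.4.4 already plans correlations and standardised mean responses for EQ-5D utility weights. Paired summaries are also detail that a statistical analysis plan often adds. The point survives because section 6.5.1 fixes a form that does not match section 6.4.1.
- **The correlation argument does not reach return to work.** Time to return has no baseline value to pair, and the version tracker records hours until return to work as the agreed primary outcome of the definitive trial. The argument concerns the clinical scores.
- **The coding of antidepressant use is not stated.** The last point is therefore conditional on yes/no coding.

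**Conclusion.** The point holds in a limited form. The protocol labels B and C together as outcomes without the intervention, although B, 43% of the planned controls, is the group whose contamination is being examined. The possible distortion is modest at low contamination (4% of the effect if a tenth of B is affected) and material at high contamination (21% if half is). Those fractions are assumed, and neither the occurrence nor the direction of bias is shown.

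For the clinical scores, the planned tables omit the change that the protocol names, its SD and the baseline/follow-up correlation, and give no SD for skewed scores. The illustrative range of 213 to 120 per arm rests on an assumed difference, power and correlation; the documents give none of these for the definitive trial. If follow-up columns include only responders while baseline columns include everyone, the contrast would also mix change with dropout, but section 6.5.1 does not say which participants enter each column.

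For antidepressant use, the rule is wrong if the item is yes/no. These are inexpensive corrections to stated text. They do not show that the feasibility study fails in its purpose.

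**What to change.** **Sections 6.1 and 7.0.** Report control outcome distributions for Groups B and C separately as well as combined. State that B, or B and C combined, will be used as power inputs only in light of the contamination comparison. Describe how the study's referral and promotion steps changed usual care at each control site, so that the next trial's designers can judge whether its controls would receive the same.

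**Section 6.5.1.** For participants with both time points, add mean change, SD of change and the baseline/follow-up correlation for PHQ-9, GAD-7 and the quality-of-life scores. Give SDs whatever the shape of the distribution, beside medians and IQRs where scores are skewed. Report antidepressant use as n (%) at each time point.

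**Cost.** A few extra table columns and a short description, with no new data collection. Each group shown alone is less precise than the two combined: the SD interval factor is 0.79 to 1.36 for C against 0.83 to 1.25 for B and C together. Keeping the combined figure beside the separate ones limits that loss.

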# 6.2 Case manager training

Training of the case managers is an important component of the intervention. We have therefore developed a two day bespoke training package. The small groups size of up to eight case managers (a maximum of two per intervention trust) will allow for in-depth training. We will base our training on our experience of running case-manager training days with an emphasis on problem solving and promotion of engagement (JS, RS) (Smedley et al. 2013) and on mental health training days for OH nurses (MH, IM) (Madan et al. 2013). We have previously shown that small group training on mental health for OH nurses results in good knowledge transfer and use of knowledge in practice, plus increased confidence and high levels of satisfaction with the training (Kirkpatrick 1994). The essential skills required of case managers are the capacity to create a supportive, empathic atmosphere in which they explore and make salient the client's own reasons for returning to work, discuss their barriers to RTW and support the client when ready, to identify an acceptable pathway to change by facilitating structured personal goal setting. This goal setting element will be orientated to increasing activities at home and gradually introducing and scaling up engagement with the employer and phased return to work.

Training for case managers will therefore comprise a number of related elements, which will be integrated in the manual and in the training.

- 1) Clinical assessment of CMHD in the OH context, delivered by a consultant occupational physician and consultant psychiatrist: symptom and functional enquiry, mental state assessment, use of standardised questionnaires (GAD-7, PHQ9), principles of the optimal treatment of CMHDs (counselling, talking therapies, drug treatment, on-line CBT in conjunction with input from a therapist), and availability of these locally, addressing and overcoming barriers to work, problem solving using a specified framework, RTW planning, including the indications for phased hours, minimising shift work, exposure to stressors at work, work volume, and the management of relationships at work.
- 2) Problem solving and motivational interviewing (MI): Case managers will be taught to deliver problem solving in the spirit of MI to promote participant engagement by RS who is experienced in teaching and delivering MI training in a variety of settings including chronic disease and OH case management.

Training will combine workshop input with follow-up individualised supervision. Case managers will be permitted to consult with the study participants when their problem solving practice has achieved pre-determined competency thresholds.

- 3) Cognitive Behavioural Therapy (CBT) skills: case managers will be coached in CBT techniques. This will be provided by a psychiatrist, but will stop short of conventional clinical CBT training, focusing instead on the use of CBT approaches (e.g. positive thought cycling) with a workplace focus. For example defusing negative cycling or rumination about problems in the workplace. We will train the case managers in risk assessment of serious self-harm or suicide in the study participants. We will build an escalation procedure into the training, which will take into account the case managers current local procedures.
- 4) Use of the study protocol and communications with line managers and GPs. Setting up a peer-support network.
- 5) Safety issues: Procedures for safeguarding vulnerable individuals, which will be dovetailed with the local procedures at the case-manager's trust.

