We will collect information about: rates of recruitment; reasons for non-participation; baseline characteristics of those eligible for inclusion; adherence to the intervention in those allocated to receive it and the management of those who are not; and rates of successful follow-up. Additionally, we will collect data on the distribution of possible outcome measures, including, reduction in anxiety/ depression, health-related quality of life, change in antidepressant use and RTW during the six month study period. Full and partial return to work will be measured by total days of sickness absence before return to work and self-reported number of hours worked. We will collect information about participants' referral to and uptake of improving access to psychological therapies (IAPT) services and the Government's Fit for Work Service We will record any protocol violations, reasons for not completing the intervention and any adverse events.

At the sponsor site (Guy's and St Thomas NHS Foundation), we will conduct further exploratory work to better understand the factors impacting on the identification and referral of employees who are on sick leave with a common mental health disorder. Where appropriate and with relevant permissions, this may include reviewing information on existing management referrals. These insights will be pooled with information obtained from the focus group interviews.

Costs of delivering the package of interventions including OH nurse time, participant and manager time and cost of training OH nurses in case management.

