### 11b Safety assessment and reporting

Lead collaborators at participating sites will be responsible for reporting all SAEs to the chief investigator as soon as they are identified. In the context of this study, SAE are defined as self-harming or attempted or completed suicide by the participants or a serious or significant deterioration in a participant's mental state. The chief investigator will then be responsible for reporting SAEs to the R&D. Reports of related and unexpected SAE will be submitted to the main REC within 15 days of the chief investigator becoming aware of the event.

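### SAEs are found passively by sites, but risk-assessment training and scheduled reviews are described only for the intervention, so non-fatal events will probably be found more often in Groups A and D

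*Protocol*

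**What the plan says.** Section 11b of the protocol sets one definition for every site: "SAE are defined as self-harming or attempted or completed suicide by the participants or a serious or significant deterioration in a participant's mental state". The route is also common: "Lead collaborators at participating sites will be responsible for reporting all SAEs to the chief investigator as soon as they are identified". It names no scheduled enquiry, no source and no time point at which anyone looks for these events. Section 6.4.1 adds only: "We will record any protocol violations, reasons for not completing the intervention and any adverse events".

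Section 6.2 puts the skills that bear on recognising such events into the case managers' training. "We will train the case managers in risk assessment of serious self-harm or suicide in the study participants", and then: "We will build an escalation procedure into the training, which will take into account the case managers current local procedures". The same syllabus covers "symptom and functional enquiry, mental state assessment, use of standardised questionnaires (GAD-7, PHQ9", and safeguarding procedures. Section 6.1 makes case managers the intervention nurses. The usual-care nurses at the three mixed trusts are not trained as case managers, and the two usual-care trusts have no case managers.

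Sections 1.0 and 5.0 list reviews at set times as a component of the intervention. Care as usual is whatever each trust already does, with no schedule set by the protocol.

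On data, the study design text in section 6.0 states: "We will collect the same data on all participants and participating centres".

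**The concern.** With passive reporting, the number of events found depends on who is looking, how well prepared they are and how often they look. All three are described more fully for Groups A and D than for B and C. The SAE definition consists of the mental-state and self-harm events that the case managers are prepared to assess.

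Adverse effects are listed in section 1.0 among the acceptability outcomes, and section 6.1 names adverse events as an outcome of the envisaged RCT. Groups B and C are the only concurrent reference for anyone who wants to put the A and D counts in context. If the feasibility study does not try out an even-handed way of collecting harms, the future trial inherits an untested and probably uneven one.

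**Working it through.** **1. The plan's own count.** From Table 1 in section 6.1:
- Care as usual: 14 + 14 + 7 + 7 + 7 = 49 (Group B 21, Group C 28).
- Intervention: 7 + 7 + 7 + 7 = 28 (Group A 21, Group D 7).
- Total: 49 + 28 = 77. The 49 agrees with section 11.0a, and 49/77 = 64%.

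**2. Ways an event could come to notice, as described.**

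| Route | Groups A and D | Groups B and C |
|---|---|---|
| SAE definition and site report (11b) | Yes | Yes |
| Nurse trained by the study in mental-state and self-harm risk assessment and escalation (6.2) | Yes | Not described |
| Reviews at set times (1.0, 5.0) | Yes | Local practice, not described |
| Content analysis of a random 40% of consultations (6.2, a fidelity check) | Yes | None described |
| Questionnaires at 0, 3 and 6 months (6.4.1) | Yes | Yes, but no rule links answers to SAEs |

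The only route common to all groups that reaches the SAE record is the passive one.

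**3. Direction.** Let the true risk be r in both arms, and let the shares of events found be s_I (intervention) and s_C (care as usual). The observed rates are r·s_I and r·s_C, so the observed ratio is s_I/s_C and r cancels. If s_I > s_C the ratio exceeds 1. The error runs against the intervention.

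**4. Illustrations only.** The protocol gives no SAE risk, contact number or detection share, so every input here is an assumption.
- With k independent contacts and recognition probability d at each, the share found is 1 − (1 − d)^k. For d = 0.3 this is 0.51, 0.66 and 0.76 at k = 2, 3 and 4. For d = 0.5 it is 0.75, 0.88 and 0.94.
- Four v three contacts: ratio 1.16 (d = 0.3) or 1.07 (d = 0.5).
- Four v two contacts: ratio 1.49 (d = 0.3) or 1.25 (d = 0.5).
- Shares set directly: 0.9/0.6 = 1.5; 0.9/0.3 = 3.0.

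**5. Counts.** True expected events are 28r and 49r.
- r = 2%: 0.56 and 0.98.
- r = 5%: 1.40 and 2.45.
- r = 10%: 2.80 and 4.90.

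At r = 5% with s_I = 0.9, the intervention shows 28 × 0.05 × 0.9 = 1.26 events. Care as usual shows 49 × 0.05 × 0.6 = 1.47, or about 0.7 if s_C = 0.3. The chance of recording no SAE at all in care as usual is (1 − 0.05·s_C)^49: 8% with full detection, 23% at s_C = 0.6 and 48% at s_C = 0.3. At these counts no ratio from step 4 could be told from chance. The practical risk is a misleading impression of few or no events under usual care.

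**The case against.** The strongest reply is that the protocol plans no comparison of harms between arms. Section 6.1 gives A and D to acceptability, costs and adherence, and B and C to outcome distributions and contamination; section 6.5.1 is descriptive. Adverse effects appear in section 1.0 beside reasons for not completing the intervention, as part of experience with it. This stands, and it limits the point to description and to the design of the next trial.

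A reader might also infer more than the documents support:
- **That usual-care nurses receive no SAE briefing.** The protocol is silent on this. Section 11b applies to all sites, and local risk procedures may exist.
- **That the SAE definition and reporting route sit inside the case managers' package.** They do not. Section 6.2 covers clinical risk assessment, escalation and safeguarding.
- **That the promise to collect the same data is contradicted.** It is naturally read as the same items for everyone, not equal detection.
- **That missed control events could hide harm from the intervention.** They work the other way: usual care looks safer and the intervention worse.
- **That a particular rate ratio follows.** It does not. The contact model is assumed throughout and fits completed suicide poorly, since that would probably come to light in any group.

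The common questionnaires, with PHQ-9 and GAD-7 as the clinical measures (section 2.4.1), give some equal view of deterioration. They go to the central research team, however, and nothing in the protocol turns an answer into an adverse-event record. The partial safeguard therefore does not close the gap.

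**Conclusion.** The point holds in a limited form. SAE capture is passive, and the described aids to detection favour Groups A and D. Self-harm, attempts and serious deterioration are likely to be under-found in Groups B and C, 64% of participants. Unequal detection is an inference from how the study is set up; the protocol does not state it, and it would weaken if sites in practice brief and review usual-care participants similarly. The direction follows if detection is better in A and D; the size is unknown. Because no harms test is planned and only a handful of events can be expected, no planned analysis is invalidated. What suffers is the descriptive account of adverse effects and the adverse-event method handed to the RCT. The change is cheap and worth making.

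**What to change.** - **Common enquiry.** In sections 11b and 6.4.1, add one identical adverse-event and SAE enquiry for every participant in all four groups at the existing 3- and 6-month questionnaire contacts. Use the same wording in both versions of the 6-month questionnaire. Do not use occupational health records as the common source: they are likely to be fuller for case-managed participants and would carry the imbalance over.
- **Common instruction.** Give all recruiting OH nurses at all six centres the same instruction on the 11b SAE definition and reporting route, and nothing more. Leave clinical risk-assessment training in the intervention package, so that usual care and the contamination assessment are not altered.
- **Reporting.** Tabulate SAEs by group and by route of detection (common enquiry or spontaneous site report), with the number answering the enquiry in each group. Base any between-group statement on the common enquiry alone.

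The cost is a short questionnaire item, a brief site instruction and a few lines of protocol text. The investigators must also settle how an answer reporting such an event is handled once received; that is a clinical matter for them. The enquiry will under-capture events in people who do not return questionnaires, possibly those who have deteriorated most, and it cannot record deaths. Site reporting must therefore continue alongside it.
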